Subjects have to be 20 to 75 years of age and have at least one maxillary edentulous posterior site requiring maxillary sinus grafting and replacement with a dental implant. Subjects will be excluded from this study if they are current smokers/use tobacco, are pregnant, have active periodontal disease, uncontrolled diabetes, any autoimmune disease, kidney disease, or liver disease or receiving radiation or chemotherapy. Finally, subjects will also be excluded if they have any type of radiographic periapical pathology such as a periapical abscess.

Attachments

Indicate the targeted/planned enrollment of the following members of minority groups and their subpopulations. Possible demographic sources: [Census Regional Analyst Edition](#), [Kentucky Race/Ethnic Table](#), [Kentucky Population Data](#).

(Please note: The IRB will expect this information to be reported at Continuation Review time for Pre-2019 FDA-regulated Expedited review and Full review applications):

Participant Demographics				
	Cisgender Man 	Cisgender Woman 	TGNB/TGE 	Unknown/Not Reported
American Indian/Alaskan Native:				
Asian:				
Black/African American:				
Latinx:				
Native Hawaiian/Pacific Islander:				
White:				
American Arab/Middle Eastern/North African:				
Indigenous People Around the World:				
More than One Race:				
Unknown or Not Reported:				

If unknown, please explain why:

There will be no restriction for race or ethnicity. Any subject that presents fitting the criteria specified in the inclusion section could participate in the study.

Indicate the categories of subjects and controls to be included in the study. You may be required to complete additional forms depending on

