- **Research Repositories:** If the purpose of this submission is to establish a Research Repository (bank, registry) and the material you plan to collect is already available from a commercial supplier, clinical lab, or established IRB approved research repository, provide scientific justification for establishing an additional repository collecting duplicate material. Describe the repository design and operating procedures. For relevant information to include, see the [UK Research Biospecimen Bank Guidance](#) or the [UK Research Registry Guidance](#).

The current study will be a single site, randomized, controlled clinical and histological investigation. Subject recruitment: May 2020 - January 2022 with 20 subjects, there will be no placebo medication at any point in the research procedures. Eligible patients will be randomly assigned to one of two treatment groups using a randomization table generated by a computer. The test group (10 sinuses) will receive Shefabone and control group (10 sinuses) will receive Bio-Oss xenograft material. Little is known about the distribution of bone quality changes in patients who receive Shefabone graft to augment the maxillary sinus. Ten subjects per group is reasonable to providing an 80% probability of estimating the true mean for bone quality and implant stability to within half a standard deviation in each group.

Attachments

Subject Recruitment Methods & Advertising

Describe how the study team will identify and recruit subjects. Please consider the following items and provide additional information as needed so that the IRB can follow each step of the recruitment process.

- How will the study team identify potential participants?
- Who will first contact the potential subjects, and how?
- Will you use advertisements? If so, how will you distribute those?
- How and where will the research team meet with potential participants?
- If applicable, describe proposed outreach programs for recruiting women, minorities, or disparate populations.
- How you will minimize undue influence in recruitment?
- Attach copies of all recruiting and advertising materials (emails, verbal scripts, flyers, posts, messages, etc.).

For additional information on recruiting and advertising:

- [IRB Application Instructions - Advertisements](#)
- [PI Guide to Identification and Recruitment of Human Subjects for Research](#)

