The PI will recruit subjects from the University of Kentucky College of Dentistry clinics. Subjects that are coming for treatment of missing maxillary teeth and have a pneumatized maxillary sinus, and match the inclusion criteria will be told about the research and offered the opportunity to participate. Only the PI outlined in this IRB application will select study participants. Selection will be inclusive of patients who give signed permission to participate.

The population's data will be identified and only the PI will have secured access to that data. The participant will be interacting with the investigator only; this will be done chairside within the UKCD periodontics clinic only.

No advertisement will be used at this time.

Attachments

Research Procedures

Describe how the research will be conducted.

- What experience will study participants have?
- What will study participants be expected to do?
- How long will the study last?
- Outline the schedule and timing of study procedures.
- Provide visit-by-visit listing of all procedures that will take place.
- Identify all procedures that will be carried out with each group of participants.
- Describe deception and debrief procedures if deception is involved.

Differentiate between procedures that involve standard/routine clinical care and those that will be performed specifically for this research project. List medications that are explicitly forbidden or permitted during study participation.

All patients who agree to take part in this study will be placed in a randomization table to determine which product they will receive and which clinician will be performing the surgery. Therefore, no one clinician will be performing the entire test or all of the control groups; it will be completely randomized.

Visit 1:

Subjects will be asked to read and sign the Informed Consent as well as encouraged to ask any questions related to the study. Subjects will sign the Informed Consent form and receive a copy of their consent. Subjects will be enrolled if they meet the inclusion criteria and none of the exclusion criteria. An oral tissue examination then been performed and a limited view CBCT scan will be taken of the maxillary arch.

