Subjects will be randomly assigned in the control and test group using a computer generated randomization table. Subjects who have compromised health, due to any of the exclusion criteria, which may affect the ability of the subject's tissues to heal, will be excluded from the study.

Visit 2:

After administration of a local anesthesia (Lidocaine 2% injection with 1:100,000 Epinephrine), a cresto-palatal incision will be performed using a 15C surgical blade at the maxillary posterior edentulous site. Full thickness muco-periosteal flap will be reflected with a vertical releasing incisions. The osteotomy will be prepared on the lateral wall of maxillary sinus area using the Piezosurgery unit. A lateral window will be open to completely reflect the Schneiderian membrane and 2 grams of the ShefaBone? (porous granules of bioactive and resorbable silica-calcium phosphate nanocomposite), graft material will be applied into the sinus site for test group and 2 grams of Bio-Oss? (bovine bone in a validated multistage purification process to remove the organic components), for control group. The grafted site will be covered with a resorbable collagen membrane to perform guided bone regeneration (GBR) and to protect the bone graft from the intrusion of undesired soft tissue growth. The flap will be secured using an interrupted suture with tension free primary closure. A second limited view CBCT will be taken as standard of care. After surgery, subjects will be given post-operative instructions.

Augmentin 875/125 mg, one tablet every 12 hours for 10 days will be prescribed. This recommendation of antibiotics will be given to each subject based on current UK College of Dentistry implant protocol and started one day before the surgery. For subjects unable to take amoxicillin for any reason, an alternative antibiotic will be prescribed, i.e. Z-PAK (Zithromax) 250mg (5 day PAK) Take 2 tablets on day one, then 1 tablet daily on days 2 through 5. Analgesic, Ibuprofen up to 600 mg every 6 hours will be prescribed as needed. Subjects will be advised to clean the surgical area gently with a Toothette® Oral Swab moistened with 0.12% chlorhexidine gluconate four times daily for two weeks.

Visit 3:

Subjects will return in two weeks after the surgical visit to have the sutures removed and for evaluation of healing.

Visit 4:

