Yes. Device(s) being tested in this study presents a potential for serious risk to the health, safety, or welfare of a subject and (1) is intended as an implant; or (2) is used in supporting or sustaining human life; or (3) is of substantial importance in diagnosing, curing, mitigating or treating disease, or otherwise prevents impairment of human health; or (4) otherwise presents a potential for serious risk to the health, safety, or welfare of a subject.

No. All devices being tested in this study do not present a potential for serious risk to the health, safety, or welfare of subjects/participants.

Complete and attach the required [Study Device Form](#), picking the "Study Device Form" for the document type. Any applicable device documentation (e.g., Manufacturer information; patient information packet; approved labeling; FDA correspondence, etc.) should be attached using "Other Device Documentation" for the document type.

Attachments

Attach Type	File Name
Study Device Form	Study Device Form 04 21 2020 - 1.pdf
Study Device Form	Study Device Form 04 21 2020 - 2.pdf

Statistical Analysis

For bone radiographic bone height analysis, ten subjects per group will provide 80% power to detect an effect size of 1.4 on newly formed bone using an independent two group t-test with a 5% two-sided significance level. An exploratory analysis was carried out to verify the normality supposition by Shapiro-Wilk. Non-parametric distribution was observed for the variables of bone and new bone percentage measurements; however, biomaterial data was classified with a Gaussian distribution. Thus, Mann-Whitney and T-test were applied for intergroup comparisons, respectively. Fisher Exact Test was performed between treatment groups. $P \leq 0.05$ was considered significant. Sigma Plot software was used for statistical analysis.

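### The eligibility list names no drug that acts on bone turnover, so users may be enrolled and can add variance and chance imbalance to the bone outcomes in arms of ten

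*Combined protocol and SAP*

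**What the plan says.** The only eligibility list is under Study Population, Inclusion and Exclusion Criteria. On age it says: "Subjects have to be 20 to 75 years of age". It excludes tobacco users, pregnant women, and patients with active periodontal disease or periapical pathology, and then "uncontrolled diabetes, any autoimmune disease, kidney disease, or liver disease or receiving radiation or chemotherapy". No medication is named apart from chemotherapy, and no bone disease is named.

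Research Procedures, Visit 1, has a healing clause, which begins: "Subjects who have compromised health, due to any of the exclusion criteria, which may affect the ability of the subject's tissues to heal". Its reach is limited to the listed criteria. The same visit enrols anyone who meets the inclusion criteria and none of the exclusions.

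The Research Procedures form carries a prompt: "List medications that are explicitly forbidden or permitted during study participation". This is the form's wording, not the sponsor's. The reply describes the anaesthetic, antibiotics, analgesic and rinse used around surgery, and forbids nothing.

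On design, subjects are "randomly assigned to one of two treatment groups using a randomization table generated by a computer", and "The test group (10 sinuses) will receive Shefabone and control group (10 sinuses) will receive Bio-Oss xenograft material". No stratification is stated. Statistical Analysis says "ten subjects per group will provide 80% power to detect an effect size of 1.4 on newly formed bone" with a two-sided 5% t-test. It compares groups by Mann-Whitney, t-test and Fisher's exact test, with no covariate. The histomorphometric outcomes are the percentages of vital bone, graft remnants and connective tissue in a core taken at five months.

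**The concern.** Vital bone and residual graft at five months are what bone formation and resorption have left behind. A drug that acts on bone turnover acts on the outcome itself. The exclusion list screens for several conditions that could disturb healing, but not for these drugs, and the age range runs to 75.

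Nothing later in the plan compensates. Background medication is not a stratification factor, a covariate or a planned subgroup. Medical histories appear only as stored source documents under Records, Privacy, and Confidentiality, with no visit attached and no stated use in the analysis. In arms of ten, one or two atypical subjects can widen the spread, or make the arms unlike by chance, enough to weaken the comparison. These subjects would also undergo the research-only steps: the assigned graft material and the core harvest.

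**Working it through.** **Inputs from the documents.** 10 per arm, standardised effect 1.4, two-sided 5% independent t-test (Statistical Analysis); computer-generated table with no stated stratification (Study Design).

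**Assumed, because the documents are silent.** The number or share of users, and a downward shift *s* of 1 to 3 SD in a user's new-bone value, where SD is that of non-users.

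**1. The plan's own figure.** Exact power uses the noncentral t with df = 2n − 2 and noncentrality d√(n/2). For d = 1.4, n = 9 gives 79.6% and n = 10 gives 84.1%. So 10 is the smallest arm size that reaches 80%. The plan's figure reproduces, and the baseline here is 84%.

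**2. How users split between arms (hypergeometric, 10/10).**
- Two users: both in one named arm, (10 × 9)/(20 × 19) = 0.237; both in the same arm, either one, 2 × 0.237 = 0.47; one in each, 0.526.
- Three users: all in one arm, 0.21.

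**3. Power at 1.4 SD by where the users fall.** Simulated t-test, 10 per arm. The better arm is the one with the truly higher mean.

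| Shift | One user: better arm | One user: other arm | One user: average | Two users: both better arm | Two users: one each | Two users: both other arm | Two users: average |
|---|---|---|---|---|---|---|---|
| 1 SD | 77% | 88% | 82% | 69% | 82% | 91% | 81% |
| 2 SD | 65% | 89% | 77% | 43% | 74% | 93% | 71% |
| 3 SD | 49% | 89% | 69% | 18% | 60% | 94% | 58% |

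The averages weight by the allocation probabilities. At 2 SD, one user gives (65 + 89)/2 = 77%. Two users give 0.237 × 43 + 0.526 × 74 + 0.237 × 93 ≈ 71%.

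**4. The same question by prevalence.** If a share p of patients are users, the SD is inflated by √(1 + p(1 − p)s²). At p = 10% and s = 2 this is √1.36 = 1.166, the effect becomes 1.4/1.166 = 1.20, and power is 72%. Over p = 5% to 20% and s = 1 to 2 SD, power runs from 82% down to 64%. Regaining 80% would take between 10 and 15 per arm.

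**5. Size of a chance imbalance.** An excess of m users in one arm moves the mean difference by m × s/10. For m = 2 and s = 1 to 2 SD this is 0.2 to 0.4 SD, or 14% to 29% of the 1.4 SD design effect.

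**6. False positives.** With no true difference and two users of shift 2 or 3 SD, rejection is about 8% or 9% if both fall in one arm. It is about 2% or 1% if they split. Averaged over random allocation it is 4.9% or 4.7%. Simulation by prevalence (10% and 20%, shift 1 to 2 SD) gives 4.9% to 5.1%.

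**The case against.** Several stronger readings are tempting, and the documents do not support them.

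- **That background drugs would drive or bias the result.** Randomisation makes exposure independent of arm, so the effect is noise and chance imbalance. Over the 1 to 2 SD range, an excess of two users accounts for part of a 1.4 SD difference, not all of it.
- **That the false-positive rate rises to 8%-9%, or power collapses to 18%.** Both figures condition on every user landing in one arm. For two users in the better arm the probability is 24%, and if both land in the other arm, power rises. The averages are the fair summary.
- **That the criteria fail the Visit 1 healing clause.** That clause promises only what the exclusion list contains.
- **That such patients must be enrolled.** Eligible patients are offered participation and the investigator selects among them. They may be enrolled; nothing compels it.
- **That the trial exposes them to two extra operations.** The plan marks most steps of both surgeries as standard of care. Only the graft material and the core are research procedures.

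Three further limits stand. The autoimmune and chemotherapy exclusions remove some steroid and oncology users. The plan assigns Mann-Whitney, not the t-test, to new-bone percentage; baseline power at 1.4 SD is then about 80%, so the t-test figures are a guide to that outcome rather than exact. The consent and device-form attachments are not in the supplied text.

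None of this closes the gap. The investigator's unwritten discretion is not a criterion, and no planned step identifies or accounts for users.

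**Conclusion.** The omission is real, and its effect is on precision. Assuming shifts of 1 to 3 SD and random allocation, one user among the 20 lowers t-test power at 1.4 SD from 84% to about 82%-69%, and two users lower it to about 81%-58%. Two users land in the same arm with probability 47%. Overall type I error stays about 5%, and there is no systematic bias.

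These sizes rest entirely on the assumed shift and number of users, since the documents supply neither. At 1 SD the loss is small; at 3 SD with two users it is serious. The safety aspect is confined to the research-only graft material and core, and cannot be quantified from the documents. This is a worthwhile, inexpensive improvement rather than a flaw that invalidates the design.

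**What to change.** - Add to Inclusion and Exclusion Criteria an exclusion for drugs that alter bone turnover. The sponsor should set the drug list and the look-back period.
- Add a medication-history check to Visit 1, before assignment. As described, Visit 1 lists consent, an oral tissue examination and a CBCT scan, so the check has to be written in rather than assumed.
- Record any such drug started between Visit 2 and Visit 5, and prespecify a sensitivity analysis that reports the histomorphometric comparison with and without those subjects.

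The cost is one eligibility line, one history check and one extra reported comparison. The downside is a slightly smaller recruitment pool for 20 subjects and slightly narrower generalisability.

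### Product and surgeon come from one table with no described balancing of product within surgeon and no surgeon term in the analysis, so surgeon balance is left to chance with 10 per arm

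*Combined protocol and SAP*

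**What the plan says.** Research Procedures: consenting patients "will be placed in a randomization table to determine which product they will receive and which clinician will be performing the surgery". The next sentence opens with Therefore and draws the conclusion that "no one clinician will be performing the entire test or all of the control groups; it will be completely randomized".

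Study Design: "Eligible patients will be randomly assigned to one of two treatment groups using a randomization table generated by a computer". The arms are fixed: "The test group (10 sinuses) will receive Shefabone and control group (10 sinuses) will receive Bio-Oss xenograft material". Visit 1 again says only that the table is computer generated. No section gives the number of clinicians, a block size, or any stratification of product by clinician.

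Statistical Analysis: "ten subjects per group will provide 80% power to detect an effect size of 1.4 on newly formed bone". The test behind that figure is a two-sample t-test, two-sided at 5%. For the comparisons themselves, "Mann-Whitney and T-test were applied for intergroup comparisons, respectively". The section also names a Fisher exact test between the arms. None of these tests includes the clinician.

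**The concern.** By randomizing the surgeon, the plan treats the surgeon as a factor that could affect the result. It then relies on chance to spread surgeons over the arms and leaves the surgeon out of the analysis. The conclusion in Research Procedures does not follow as a guarantee. The condition it names, that no one clinician does a whole arm, is also too weak to protect the comparison: a clinician could do 7 cases in one arm and 3 in the other and still satisfy it.

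Two things are at stake in a trial of 20. In the one table actually used, a difference between surgeons can shift the observed difference between materials. And whatever variance surgeons contribute stays in the error term of an unadjusted test.

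**Working it through.** **Inputs from the documents.** 10 per arm; effect size 1.4; two-sided 5%; two-group t-test. **Assumed, because the documents are silent:** K = 2 to 5 clinicians, each drawn independently with equal probability, and a span of 0.5 to 2 within-clinician SD between the lowest and highest clinician, with clinicians evenly spaced.

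**1. The plan's own figure.** The non-centrality is 1.4 × √(10×10/20) = 1.4 × √5 = 3.13. With 18 degrees of freedom, non-central t power is 84.1%; with 9 per arm it is 79.6%. Ten is the smallest arm size that reaches 80%, so the figure reproduces.

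**2. The literal promise.** The chance that one clinician does a whole arm is 1 − (1 − K⁻⁹)². This is 0.39% for K = 2, 0.010% for K = 3 and under 0.001% for K = 4.

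**3. Chance imbalance.** With K = 2 and X and Y the first clinician's counts in the two arms, X − Y + 10 is binomial(20, ½), so P(|X − Y| ≥ 3) = 26.3% and P(|X − Y| ≥ 4) = 11.5%. For K = 3 and 4, from 200,000 simulated tables:

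| Clinicians | Some caseload differs by ≥3 | by ≥4 |
|---|---|---|
| 2 | 26% | 12% |
| 3 | 46% | 22% |
| 4 | 51% | 22% |

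**4. What one imbalance does.** Take two clinicians 1 SD apart, one with 7 test and 3 control cases and the other with 3 and 7. The observed effect shifts by (7 − 3)/10 × 1 SD = 0.4 SD, and 0.4/1.4 = 29% of the design effect.

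**5. Bias and type I error.** Over repeated tables the mean error of the unadjusted estimate is about zero (within 0.011 SD in simulation), and unadjusted type I error is 0.048 to 0.054.

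**6. Power as planned.** Read 1.4 as within-clinician SD. At a 1 SD span, two clinicians sit at ±0.5, adding variance 0.25. The total SD is √1.25 = 1.118 and the effect is 1.4/1.118 = 1.25 total SD. With four clinicians at ±0.5 and ±1/6, the added variance is (0.25 + 0.028)/2 = 0.139, the total SD is 1.067 and the effect is 1.31. With balance and a clinician term, the non-centrality returns to 3.13 on 20 − 1 − K degrees of freedom: 83.9% for K = 2 and 83.3% for K = 4. The other columns are simulated, 12,000 runs each:

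| Clinicians, span | As planned | Clinician term, no balancing | Balance plus term |
|---|---|---|---|
| 2, 0.5 SD | 82% | 82% | 84% |
| 2, 1 SD | 75% | 82% | 84% |
| 4, 1 SD | 79% | 76% | 83–84% |
| 2, 2 SD | 55% | 82% | 84% |
| 4, 2 SD | 67% | 76% | 83% |

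Balancing without the clinician term makes the test conservative: at a 1 SD span, type I error is 0.028 with 2 clinicians and 0.036 with 4.

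**7. The other reading of 1.4.** The plan does not say which SD it uses. If it is the total SD, power as planned is 84.1%, and balance plus adjustment raises it to about 87% or 91% if clinician explains 10% or 20% of the variance.

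**8. Cost if clinician has no effect.** Power is 83.9%, 83.3% and 82.9% with 2, 4 and 5 clinicians (17, 15 and 14 degrees of freedom), against 84.1%. The largest loss is 84.1 − 82.9 = 1.2 points.

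**The case against.** Three stronger readings are tempting, and the documents support none of them.

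- A reader might infer that the scheme fails to deliver what it promises. The promise is narrow, and it holds in at least 99.6% of tables with two or more equally likely clinicians. Only the guarantee is missing.
- A reader might infer that surgeon effects will systematically pass for material effects. They will not: clinician is drawn at random, expected bias is zero and type I error stays near 5%.
- A reader might infer from the phrase about complete randomization that product is unrestricted and the arms may come out unequal. The plan fixes the arms at 10 and 10, which points to some restriction on product. The text is silent on blocking; it does not rule it out.

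The strongest remaining defence is that the surgeon effect may be small. No section gives its size, and several features limit it: a common departmental surgical protocol, the same graft weight in both arms, core harvest based on a printed template, and blinded radiographic reading. At a 0.5 SD span with 2 clinicians the gain is about 2 points, and on the total-SD reading of 1.4 the plan already exceeds 80%. This defence stands as a limit on the size of the point. It does not remove it, because the sponsor chose to randomize the surgeon and the better allocation costs almost nothing.

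**Conclusion.** The point holds as a cheap improvement in precision; it is not a validity defect. Surgeon balance is left to chance in a 20-patient trial, and the analysis cannot recover what is lost. An imbalance of 3 or more patients for some clinician is likely enough to matter, at about one table in four with 2 clinicians and one in two with 4. The power gain from balance plus adjustment is about 9 points (2 clinicians) or 4 to 5 points (4 clinicians) at a 1 SD span, and only 1 to 3 points at most at 0.5 SD. These sizes rest on assumed clinician numbers, equal and independent assignment, and an assumed spread between clinicians.

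**What to change.** 1. Fix and state the number of clinicians before the table is generated, and say whether the assigned clinician performs the grafting, the core harvest, or both.
2. Set caseloads in the table so that each clinician has equal, or as near equal as possible, numbers of test and control cases, with totals of 10 and 10. For example, 5 and 5 per arm with two clinicians, 4, 3 and 3 with three, or 3, 3, 2 and 2 with four. Blocking within caseloads that are themselves drawn at random would not secure the 10 and 10.
3. Include clinician as a factor in the linear model, or use a clinician-stratified Wilcoxon test where a rank test is planned.
4. Adopt 2 and 3 together. With four clinicians at a 1 SD span, the term without balance lowers power from 79% to 76%; balance without the term makes the test conservative.
5. Replace the Therefore sentence with a description of this allocation.

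If the table is already in use, report cases by clinician and arm and give the clinician-adjusted estimate as a sensitivity analysis.

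Cost: a different table and one model term, with no change to treatment or sample size. The term uses K − 1 degrees of freedom, about 1 point of power at most with up to 5 clinicians if clinician has no effect. Fixed caseloads also make a clinician's last assignments easier to guess, so someone who does not enrol patients should hold the table.
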